## **Pooling**

The results from the 25 completed data sets obtained in the analysis step are combined for the inference. The pooled estimate of the multiplicity adjusted p-value for testing H0 vs H1 will be the median of the individual multiplicity adjusted p-values from the 25 completed data sets. The pooled estimate of the response rate along with its standard error and 95% CI for each dose level will be obtained using the method developed by Rubin (1987). The following is an example of SAS programming code to be implemented.

The null hypothesis H0 (Section 5.1.2) will be rejected and a statistically significant trend (i.e., an upward slope) of the fibrosis response across Aldafermin doses will be established if

- the pooled estimate of the multiplicity adjusted p-value obtained from the MI inference is ≤ 0.05 and;
- the pooled estimate of the response rate for Aldafermin 3 mg is higher than that for placebo.

The ITT analysis set will be used for these analyses.

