12.5 Efficacy Analyses

12.5.1 Primary Efficacy Analysis

The primary efficacy endpoint for this study is the histologic response at Week 24, defined as a subject achieving an improvement in liver fibrosis greater than or equal to one stage (NASH CRN fibrosis score) with no worsening of steatohepatitis (defined as no increase in NAS for ballooning, inflammation, or steatosis) after 24 weeks of treatment.

Subjects with two biopsies (baseline and post-baseline) will be considered for this analysis only if the second biopsy is taken after at least 12 weeks (i.e., 50% of the intended 24-week treatment period) of treatment on study drug. For the primary efficacy analysis, missing histologic responses at Week 24 will be imputed using a multiple imputation (MI) method under the assumption of missing at random. The details of the MI method will be provided in the SAP.

The primary efficacy endpoint will be analyzed using the MCP-Mod (Multiple Comparison Procedure – Modelling) approach to assess the dose-response relationship. Within the framework of the MCP-Mod procedure, the null hypothesis of no dose-response will be tested at the 5% significance level against the alternative hypothesis that there is a dose-response. The details of the MCP-Mod approach will be provided in the SAP.

Sensitivity analyses will include imputations with missing histologic responses as both responders and non-responders, and analysis with the assumption of missing not at random (e.g., pattern mixture models).

The primary efficacy analyses will be performed using the ITT population. The Full-Analysis and PP populations will be used as sensitivity analyses.

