## 1.3 Sample Size

The sample size for this study is determined based on power simulations for the dose-response testing for the primary efficacy endpoint – the liver fibrosis response (Section 5.1.1). The simulations were originally performed using a generalized MCP-Mod (multiple comparison procedure - modelling) approach (Pinheiro 2014) and those results are presented in the study protocol. The simulation results (Table 1) in this SAP were obtained using a different MCP-Mod approach (Klingenberg 2009) as this approach will be used for both dose-response testing and estimation for the primary efficacy endpoint.

The assumptions about the liver fibrosis response rate for the 4 treatment groups are the same as those in the protocol. Specifically, assuming that the liver fibrosis response rate is 15% for placebo and 50% for Aldafermin 3mg, respectively, it is demonstrated that a total sample size of 152 subjects (38 subjects per treatment group) will provide at least 85% power to detect a positive dose-response trend (i.e., an upward slope) at the 5% significance level (two-sided) under 6 different dose-response scenarios as shown in Table 1 (the last 6 rows). To account for potential premature discontinuation of the study subjects, a 15% drop-out rate at Week 24 is also assumed in all these simulations (i.e., only 32 subjects per group were used in these simulations).

In addition, simulations were also performed under the assumption of no dose effect (i.e., response rate=15% for all 4 treatment groups) to assess the type I error rate control of the MCP-Mod approach (first row in Table 1).

Table 1. Power Simulations for Dose-Response Testing

Liver Fibrosis Response Rate				
Placebo	Aldafermin 0.3 mg	Aldafermin 1 mg	Aldafermin 3 mg	Power
15%	15%	15%	15%	5%
15%	16%	19%	50%	92%
15%	18%	30%	50%	90%
15%	20%	42%	50%	93%
15%	32%	39%	50%	85%
15%	36%	45%	50%	87%
15%	43%	48%	50%	90%

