#### 2.2 Data Conventions

The following data conventions will be used for all analyses described in this SAP.

- All subject-level data will be provided in data listings, unless stated otherwise.
- Study day will be calculated as:
  - o visit date first dose date, for screening visits;
  - o visit date first dose date + 1, for post-baseline/treatment visits.
- Baseline value will be defined as the last available, valid, non-missing assessment reported before the start of first study drug administration. The randomization date (and time, if available) will be used if the study drug start date is missing or not available for any reason.
- Change from baseline (change) is calculated as follow-up baseline. Percent (or relative) change from baseline (percent/relative change) is calculated as 100 × (change from baseline/baseline).
- Descriptive statistics including the number of non-missing observations (n), arithmetic mean (mean), standard deviation (SD), median, minimum (min), and maximum (max) will be presented for continuous endpoints. Frequency and percentage distribution will be presented for categorical endpoints. Kaplan-Meier estimates will be presented for time-to-event endpoints if applicable.
- Continuous endpoints will be analyzed using an analysis of variance (ANOVA) or analysis of covariance (ANCOVA) model. Ordinal categorical endpoints will be analyzed using a Wilcoxon rank-sum test. Nominal categorical endpoints will be analyzed using a Pearson's Chi-square test or Cochran-Mantel-Haenszel (CMH) test (A Fisher's exact test will be used if ≥ 25% of the cells have expected counts < 5). Time-to-event endpoints will be analyzed using a (stratified) log-rank test and Cox's proportional hazards model.

- Type III sums of squares will be used for all ANOVA and ANCOVA models.

- The level of statistical significance used for all statistical tests will be 0.05, unless stated otherwise. Statistical hypotheses for the primary efficacy analyses and the associated sensitivity analyses will be tested for statistical significance with two-sided alternatives, and one-sided alternatives will be used for all secondary and other efficacy analyses. All confidence intervals (CIs) will be two-sided, unless stated otherwise.
- Data from unscheduled visits will be presented in data listings, but will not be used for statistical analysis/summaries.

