#### **Imputation**

Missing fibrosis responses are imputed 25 times to generate 25 complete data sets. The imputed values will be obtained using a logistic model with fixed effects for treatment group and baseline fibrosis stage. At the end of this step, all the 25 complete data sets contain the same non-missing values while the missing values are replaced by imputed values. The following is an example of SAS programming code to be implemented.

The random seeds to be used for this and all subsequent analyses are provided in Appendix C.

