#### Analysis

Each of the 25 competed data sets will be analyzed using the MCP-Mod approach described in Section 5.1.3. The SAS programming code to be implemented for this approach is provided in Appendix B. Results to be obtained from each data set include the multiplicity adjusted p-value for each candidate model (macro MCP), the point estimate of the response rate  $\hat{F}(x)$  (E4) for each dose level and the standard error for  $\hat{F}(x)$  (macro Mod). The standard error will be estimated by the sample standard deviation obtained from the bootstrap distribution of the point estimate (E4).

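### Taking the median p-value over 25 imputed data sets leaves imputation uncertainty out of the primary test: with about 15% missing, its two-sided size is about 7–8% instead of 5%, and false upward claims rise from 2.5% to about 4%

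*SAP*

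**What the plan says.** - **Level.** SAP 1.3 claims "power to detect a positive dose-response trend (i.e., an upward slope) at the 5% significance level (two-sided". SAP 2.2 repeats the sidedness: "Statistical hypotheses for the primary efficacy analyses and the associated sensitivity analyses will be tested for statistical significance with two-sided alternatives".
- **Imputation (SAP 5.1.5).** Missing responses are filled in 25 times under missing at random: "The imputed values will be obtained using a logistic model with fixed effects for treatment group and baseline fibrosis stage".
- **Pooling (SAP 5.1.5).** "The pooled estimate of the multiplicity adjusted p-value for testing H0 vs H1 will be the median of the individual multiplicity adjusted p-values". Rubin's method is used in the same paragraph, but only for the response rate at each dose, its standard error and its confidence interval.
- **Decision.** H0 is rejected if the median p-value is at most 0.05 and "the pooled estimate of the response rate for Aldafermin 3 mg is higher than that for placebo".
- **Type I error check.** Row 1 of SAP Table 1 reports 5% with a 15% response rate in every group. For drop-out, "only 32 subjects per group were used in these simulations". No imputation or median step is described.
- **What counts as missing.** Under Protocol 12.5.1, a subject with two biopsies is considered "only if the second biopsy is taken after at least 12 weeks" of treatment.

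**The concern.** Every completed data set is tested as though 38 biopsies per arm had been read. The imputation model contains only arm and fibrosis stage, so it adds almost no information beyond the biopsies actually observed. The median over 25 data sets smooths out the noise of a single imputation but does not widen the test for the information that is missing. The SAP therefore carries between-imputation variance for its estimates and leaves it out of the one test that decides the trial.

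The stated level of the primary test then no longer holds, and the size of the error depends on a missing share that is unknown in advance. Row 1 of Table 1 gives false reassurance, because it describes a test on 32 subjects per group and not the rule that will be applied.

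**Working it through.** **Inputs.** 38 per arm, 1:1:1:1, two-sided 5%, placebo 15% and 3 mg 50%, 15% drop-out or 32 per group (SAP 1.3); 25 imputations on arm and stage (SAP 5.1.5); F3 share near the 35% minimum (Protocol 12.2), set at 13 of 38 per arm in the main simulation. The candidate models are not readable, so the six Table 1 shapes stand in for them. A second set (linear, log, square root, Emax-type, quadratic) was used as a check.

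**Step 1: reproduce Table 1.** A permutation test on the largest absolute contrast, with 32 per arm and no imputation, gives 5.0% under the null (2.6% with the direction condition). Power is 93.7/91.2/93.5/85.1/88.2/90.0%, against the SAP's 92/90/93/85/87/90%: all within 2 points. A one-sided 5% test gives 92–97% and does not reproduce the table. The stand-in test is therefore close enough, and the two-sided reading is the one that fits.

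**Step 2: formula for one contrast.** With a fraction f missing and an uninformative imputation model, the averaged contrast has the variance of the observed subjects only, but the test uses the variance for 38. The test statistic then has variance 38/observed = 1/(1 − f), and the true size is

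2 × (1 − Φ(1.96 × √(observed/38))).

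For 6 missing: √(32/38) = 0.918; 1.96 × 0.918 = 1.80; size = 7.2%.

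In reverse, a true 5% needs a nominal |z| of 1.96 × √(38/32) = 2.14, which is a nominal p of about 0.033.

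**Step 3: simulate the SAP rule.** Logistic imputation with posterior draws, 25 imputations, permutation p-values, 20,000 null trials per setting. Ranges cover null response rates of 15% and 25%, and taking the median either per candidate model or after choosing the smallest p-value.

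| Missing per arm | Formula, one contrast | Two-sided size | Full rule (p ≤ 0.05 and 3 mg above placebo) |
|---|---|---|---|
| 0 of 38 | 5.0% | 4.8% | 2.4–2.5% |
| 2 (5%) | 5.6% | 5.4–5.9% | 2.5–3.0% |
| 4 (10.5%) | 6.4% | 6.7–6.9% | 3.3–3.4% |
| 6 (15.8%) | 7.2% | 7.8–8.3% | 3.8–4.1% |
| 8 (21%) | 8.2% | 9.0–9.7% | 4.4–4.7% |

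**Step 4: vary the set-up.**
- A separately programmed simulation with 40,000 trials per setting gives 7.4–8.0% and 3.7–3.9% at 6 of 38 missing, over both candidate sets.
- With 15% missing on average in each arm, null rates from 10% to 30% give 7.0–8.1% and 3.5–4.0%.
- Uneven missingness (10/13/17/20% and 5/10/20/25% across arms) gives 7.8% and 8.3% two-sided, taking the median of the overall p-value.
- A normal-theory test with Beta-posterior imputation gives 8.3–8.4%, and 4.2% for the full rule.

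**Step 5: pool properly.** Replace each contrast's variance U by U + (1 + 1/25)B, where B is the between-imputation variance, and refer the largest |z| to its multiplicity-adjusted critical value. At about 15% missing and a 15% null rate, the separately programmed simulation gives a size of 4.0–4.5% and false upward claims of 2.1–2.4%; the other simulations give a size of 4.3–5.1%. The test becomes conservative at low response rates (3.5% at a 10% null rate). With uneven missingness the size is 4.3%.

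| Power by Table 1 scenario | 1 | 2 | 3 | 4 | 5 | 6 |
|---|---|---|---|---|---|---|
| SAP Table 1 | 92% | 90% | 93% | 85% | 87% | 90% |
| Median rule | 95% | 94% | 96% | 90% | 92% | 94% |
| Rubin pooling | 93% | 91% | 93% | 86% | 88% | 90% |

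Part of the median rule's apparent extra power comes from its inflated size.

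**The case against.** **The full rule never exceeds 5%.** A significant result in the wrong direction cannot reject H0, and the full-rule rates stay at or below 4.7% up to 21% missing. That is true, and the full-rule figure is the one that matters for the claim. But the SAP sets a two-sided 5% test and adds a direction condition, which implies 2.5% for an upward claim. No document states 2.5%. The Protocol gives 5% without sidedness, but its Section 12 says the SAP prevails. The two-sided test also misses the level the SAP states for it.

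**Drop-out is not the same as missing.** The early-withdrawal visit includes a biopsy (Protocol 9.2.9), and it counts after 12 weeks of treatment. Some drop-outs will therefore supply a response, while refused or unreadable biopsies work the other way. At 5% missing the error is small: 5.4–5.9% two-sided and 2.5–3.0% for the full rule. This part stands, so the size is conditional on the missing share.

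**Other analyses give protection.** The dose-level estimates are pooled by Rubin's method. The per-protocol set requires paired biopsies, and responder, non-responder and missing-not-at-random analyses are planned. These help a reader to judge the result but do not change the p-value that decides it.

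**Much of the method is unreadable.** The exact test statistic could not be run. It may also be stated there how p-values from several candidate models are combined, so no fault is found on that point; the inflation appears under both readings. It comes from the pooling step and hardly moves with the candidate set.

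**This is a phase 2b trial.** That limits the consequence but is no reason to keep a test that misses its stated level.

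**Conclusion.** The concern holds. The median of completed-data p-values does not keep the level the SAP sets for its primary test. At about 15% missing, the two-sided size is about 7–8% instead of 5%. False upward claims are about 4% instead of the implied 2.5%, a factor of 4/2.5 = 1.6. At that missing share, a median p-value between about 0.03 and 0.05 would be declared significant although its calibrated value is above 0.05.

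This rests on three assumptions: missing at random, stand-in candidate shapes, and a missing share equal to the SAP's drop-out figure. The direction of the error does not depend on the candidate shapes; its size depends mainly on the missing share. The sample size is not called into question, because Table 1's power is about right for a properly pooled test.

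**What to change.** Replace the median rule in SAP 5.1.5 before unblinding. In each completed data set, compute the dose-group estimates and their covariance. Pool them by Rubin's rules, form the candidate-model contrasts, and apply the multiplicity-adjusted test to the pooled contrasts. Keep the direction condition.

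An alternative is to repeat the imputation inside each permutation, so that the reference distribution includes it. The evidence for it is thinner:
- Size was 4.4% (4,000 trials, standard error 0.3 points) and 5.6% (2,500 trials, standard error 0.5 points) at null rates of 15% and 25%.
- Power was 92/86/90% in scenarios 1, 4 and 6, from 700 trials each.
- It was not tested with missingness that differs by arm. That could arise here, because subjects whose LDL-C stays uncontrolled are withdrawn (Protocol 9.4.14).

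A fixed stricter cut-off is not advised. The value that restores 5% moves with the missing share: about 0.036 at 10% missing, 0.03 at 15% and 0.021–0.025 at 20%.

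Re-run Table 1, including the null row, with 38 randomised per group, 15% missing, and the imputation and pooling steps in the simulation.

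The cost is SAP wording and modest program changes, with no extra subjects. Power falls by about 2 to 4 points against the median rule, and the stated minimum of 85% is still met.

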## 5.1.6 Sensitivity Analyses

# 5.2 Secondary Efficacy Analyses

Secondary efficacy analyses will include treatment group comparisons of the fibrosis response (the primary efficacy endpoint) between each Aldafermin dose and placebo as well as the analyses of the following secondary efficacy endpoints:

- Subjects with resolution of NASH defined as an NAS score of 0 or 1 for inflammation and 0 for ballooning, with no worsening (compared to baseline) of fibrosis as determined by the NASH CRN criteria at Week 24
- Subjects with combined response of fibrosis improvement and NASH resolution, defined as subjects with an improvement in liver fibrosis by ≥ 1 stage with no worsening of steatohepatitis (no increase in NAS for ballooning, inflammation, or steatosis) and resolution of NASH as determined by the NASH CRN criteria at Week 24
- Subjects with improved, no change, and worsening of the following histological assessments at 24 weeks compared to baseline
  - o Fibrosis stage
  - NAS (total score and individual components)
- Subjects with the following changes in LFC by MRI-PDFF at Week 24:
  - o Normalization of LFC (defined as LFC < 5%)
  - $\circ \geq 5\%$  decrease from baseline in LFC
  - $\circ$   $\geq$  30% relative decrease from baseline in LFC
- Change and percent change from baseline to Week 24 in the following:
  - LFC by MRI-PDFF
  - o ALT, AST, total bilirubin, ALP, and gamma glutamyl transpeptidase (GGT)
  - Total cholesterol, high density lipoprotein cholesterol (HDL-C), LDL-C, and triglycerides
  - Lipoprotein particles
  - o Homeostasis model assessment-estimated insulin resistance (HOMA IR)
  - o N-terminal Type III collagen (Pro-C3)
  - o Total ELF Score and individual components (hyaluronic acid, PIIINP, TIMP-1)
  - o 7 alpha hydroxy 4 cholesten 3 one (C4) and serum bile acids (total and individual bile acids)
  - 0
- Subjects with normalization (i.e., values within the normal range) of ALT and AST at Week 24

For binary efficacy endpoints (i.e., responders), treatment group comparisons between each Aldafermin dose and placebo will be performed using the Cochran-Mantel-Haenszel (CMH) test stratified by baseline fibrosis stage. The treatment group difference of the response rates along with the corresponding 90% CI will be provided. The 90% CI will be constructed using the normal approximation method.

For continuous efficacy endpoints, change and percent change from baseline will be analyzed using an analysis of covariance (ANCOVA) model with effects for treatment, baseline fibrosis stage and baseline outcome value as a covariate. Within the framework of the ANCOVA model, a point estimate of the treatment group difference between each Aldafermin dose and placebo will be provide along with the corresponding one-sided p-value and 90% CI.

All secondary efficacy analyses will be performed using the ITT analysis set. FAS and PP analysis sets will be used as sensitivity analyses. The missing data methods and sensitivity analyses described for the primary efficacy endpoint in Section 5.1 (for ITT and FAS analysis sets) will be used for the following histological endpoints:

- Fibrosis response
- NASH resolution
- Combined response of fibrosis improvement and NASH resolution

All statistical tests for the secondary efficacy analyses will be performed using a one-side test at the significance level of 5%, and no multiplicity adjustment will be made among these secondary efficacy analyses.

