9.4.14 Lipid-Lowering Therapy Assessment

LDL-C will be evaluated at all study visits for possible increases in lipid levels associated with aldafermin administration. Rosuvastatin will be started in subjects meeting specific LDL-C level criteria at Week 2. Rosuvastatin and matched placebo are over-encapsulated in bottles of 35 capsules ([Section 10.4.2](#)). Initiation and ongoing dose adjustments of rosuvastatin will be managed by an unblinded third-party Medical Monitor and through the [REDACTED]. Lipid levels will be blinded to the sponsor and site. Initiation and dose adjustments will be determined by the lipid levels collected at Weeks 2, 4, 8, 12, and 18. LDL-C samples will be analyzed and reported to the third-party Medical Monitor. Bottles of rosuvastatin and/or matching placebo will be dispensed at each study visit through Week 18 (statin naïve) or Week 24 (statin experienced) as instructed through [REDACTED] [REDACTED] [REDACTED]. The subject will be sent home from their clinic visit with the IVRS assigned bottle(s) and instructed to refrain from dosing until told from which bottle or bottles to dose by the study site. The third-party Medical Monitor will review the LDL-C level and assign the dose of rosuvastatin [REDACTED] [REDACTED] based on the dosing algorithm ([Appendix 3](#)). The site will subsequently communicate to the subject the assigned bottle(s) and dosing should be immediately initiated.

Subjects who have not responded adequately to rosuvastatin (defined as >100 mg/dL and > 15 mg/dL above their Day1 LDL-C level), and who are currently receiving their maximum tolerated rosuvastatin dose, will be considered for additional lipid-lowering therapy (ezetimibe). The third-party Medical Monitor will contact the site regarding any subject meeting this criterion. Ezetimibe will be prescribed and taken as second-line treatment per investigator judgement and approval from the Sponsor Medical Monitor or designee. Rosuvastatin therapy should be continued as assigned. Ezetimibe should be used in accordance with the FDA-approved package insert ([Appendix 7](#)). The subjects should also continue aldafermin/matched placebo through EOT as assigned.

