12.5.2 Secondary Efficacy Analyses

Secondary efficacy analyses include the analyses of the primary efficacy endpoint (i.e., histologic response at Week 24) based on pair-wise comparisons between treatment groups and the analyses of the secondary efficacy endpoints.

All binary efficacy endpoints (i.e., responders) will be analyzed using a Cochran-Mantel-Haenszel (CMH) test stratified by baseline fibrosis stage.

All continuous efficacy endpoints will be analyzed using an analysis of covariance (ANCOVA) model with effects for treatment, baseline fibrosis stage and baseline outcome value as a covariate.

All secondary efficacy analyses will be performed using the ITT population. Full-Analysis, and PP populations will be used as sensitivity analyses.

No multiplicity adjustment will be made between the primary and secondary efficacy analyses to control the experiment-wise type I error rate, and thus all secondary efficacy analyses are exploratory in nature.

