Low density lipoprotein cholesterol (LDL-C) will be evaluated at Weeks 2, 4, 8, 12 and 18 in all subjects for possible increases in lipid levels associated with Aldafermin administration. In statin naïve subjects, rosuvastatin will be started in subjects meeting specific LDL-C level criteria at Week 2. In statin experienced subjects, rosuvastatin (10mg OD in non-Asians and 5mg in Asians) will be started at Week 2. Rosuvastatin and matched placebo are over encapsulated to maintain the blind at the sites and with the sponsor study teams. Initiation and ongoing dose adjustments of rosuvastatin/matched placebo will be managed by an unblinded third-party medical monitor and through the ....... The sponsor and study sites will be blinded to LDL-C values and the specific rosuvastatin dosing decisions as outlined in Section 9.4.14 of the protocol. Subjects who have not achieved an adequate response or cannot tolerate rosuvastatin as defined in Section 9.4.14 of the protocol will be considered for the addition of ezetimibe as second-line lipid management therapy. Ezetimibe 10 mg tablets can be administered with or without food at the same time as rosuvastatin and Aldafermin or as monotherapy. Subjects whose LDL-C values are not adequately managed by their maximum tolerated rosuvastatin dose plus ezetimibe will be discontinued from study and an early withdrawal study visit will be completed. The follow-up/end-of-study (EOS) visit should be scheduled for 6 weeks after the early withdrawal study visit.

Rosuvastatin or matching placebo will be dispensed at each study visit through Week 18 (statin-naïve) or Week 24 (statin experienced). If the subject is taking over-encapsulated rosuvastatin or matched placebo, evaluate tolerability and continue therapy to Week 24 if statin naïve or Week 30 if statin experienced.

All subjects will return to the clinic at Week 25 for post-treatment LDL-C assessment. Subjects who have an LDL-C value of >100 mg/dL and > 15 mg/dL above their Day 1 value at Week 25 will be re-assessed at Week 30. Subjects who have an LDL-C value of > 100 mg/dL and >15 mg/dL above their Day 1 value at Week 30 will have an additional 4-week follow-up visit to confirm their LDL-C value is  $\leq$  100 mg/dL or  $\leq$  15 mg/dL above their Day 1 value.

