## 5.4 Subgroup Analyses for Efficacy Endpoints

The primary and secondary efficacy endpoints will be summarized with descriptive statistics by baseline fibrosis stage (F2 or F3) and by baseline statin use (experienced or naive). No inferential statistics will be provided for the subgroups.

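### The lipid ANCOVA leaves out baseline statin status, an already collected factor that sets the Week 2 rosuvastatin rule and the rosuvastatin stop time; the cost is modest precision, not bias

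*SAP*

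**What the plan says.** SAP 5.2 gives a single model for change and percent change from baseline in all continuous secondary endpoints: an "analysis of covariance (ANCOVA) model with effects for treatment, baseline fibrosis stage and baseline outcome value as a covariate". Protocol 12.5.2 lists the same terms. The endpoints under this model include "Total cholesterol, high density lipoprotein cholesterol (HDL-C), LDL-C, and triglycerides", with lipoprotein particles as the next item. SAP 5.3 repeats the analyses at the other applicable visits.

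Statin status is defined at screening in the protocol's inclusion criteria. SAP 1.1 gives the two groups different Week 2 rules. For one group, "In statin experienced subjects, rosuvastatin (10mg OD in non-Asians and 5mg in Asians) will be started at Week 2". For the other, "In statin naïve subjects, rosuvastatin will be started in subjects meeting specific LDL-C level criteria at Week 2". The scheduled end of rosuvastatin also differs: Week 24 for naive subjects, Week 30 for experienced subjects.

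In the SAP's efficacy analyses, statin status appears only in 5.4, where the endpoints are summarised "by baseline statin use (experienced or naive). No inferential statistics will be provided for the subgroups".

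The stratification factor named in Protocol section 7 is baseline fibrosis stage. Part of Protocol 12.2 is blacked out, and nothing is inferred from that.

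**The concern.** Experienced subjects enter on a statin, so their Day 1 lipids are on-treatment values. At Week 2 all of them move to study rosuvastatin with no LDL-C condition. Naive subjects enter off statins and can only have one added. Two subjects with the same Day 1 LDL-C, one on and one off a statin, therefore have different scheduled lipid management whatever arm they are in. Baseline LDL-C reflects part of this, but need not carry all of it. By contrast, the documents give no link between fibrosis stage, which is in the model, and lipid treatment.

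The contrast is sharpest at Week 30, when only experienced subjects are scheduled still to be on rosuvastatin.

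A known effect of the drug on cholesterol is part of the protocol's rationale (5.4), and SAP 6.3 treats laboratory data descriptively. This ANCOVA is thus the only inferential lipid comparison visible in the plan. If status predicts lipid change, leaving it out makes the intervals wider than they need be. It also leaves any chance difference in statin mix between a dose arm and placebo unadjusted. All three doses are compared with the same placebo arm, so an unusual placebo mix would move all three estimates the same way.

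**Working it through.** **The plan's own figures.** The documents state no SD, effect size or power for any lipid endpoint, so there is no lipid figure to reproduce. The stated power concerns the primary test. A maximum-contrast test on proportions (32 per arm, two-sided 5%, contrasts built from the six SAP scenarios because the candidate models are not shown) gives 86-93% against the stated 85-93%. This supports using 32 per arm below and says nothing about lipids.

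**Inputs from the documents.** 38 randomized and 32 analysed per arm (SAP 1.3); secondary tests one-sided at 5% (SAP 5.2).

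**Assumed inputs.** Share experienced p = 0.3 to 0.5. Experienced-minus-naive difference in lipid change, given baseline, d = 0.25 to 1.0 residual SD.

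**Step 1: precision.** Without the term, residual variance is multiplied by 1 + p(1−p)d². Adding the term multiplies the interval width by 1/√(1 + p(1−p)d²).

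| d | narrowing, p = 0.3 | p = 0.4 | p = 0.5 |
|---|---|---|---|
| 0.25 | 0.6% | 0.7% | 0.8% |
| 0.50 | 2.5% | 2.9% | 3.0% |
| 0.75 | 5.4% | 6.1% | 6.4% |
| 1.00 | 9.1% | 10.2% | 10.6% |

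Example: p = 0.5, d = 1 gives 0.25 × 1 = 0.25 and 1/√1.25 = 0.894, a cut of 10.6%.

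**Step 2: power, for scale.** Take an assumed treatment effect of 0.6 SD. With the term, 0.6/√(2/32) = 2.40 and Φ(2.40 − 1.645) = 0.775. Without it, power is about 0.75-0.76 at d = 0.5 and 0.69-0.70 at d = 1.0.

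**Step 3: LDL-C units.** Assume 40% experienced, residual SD 25 mg/dL, 32 per arm, and mean baseline 95 (experienced) and 120 (naive) mg/dL with SD 28. If the groups differ by 20 mg/dL (0.8 SD), simulation gives an SE for the treatment difference of about 6.7 without the term and 6.4 with it, a variance ratio of about 0.90. The formula in Step 1 gives 1/(1 + 0.24 × 0.64) = 0.87. The simulated gain is smaller mainly because baseline LDL-C already absorbs part of the difference. At 10 mg/dL the variance ratio is 0.97-0.99.

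**Step 4: chance imbalance.** The between-arm difference in the share experienced has SD √(2p(1−p)/38), which is 0.105 at p = 0.3 and 0.115 at p = 0.5. Its 95% range is about ±21 to ±23 points. At p = 0.4 the exact binomial chance that a given dose arm differs from placebo by at least 10 points is 41% (34-38% by the normal approximation over p = 0.3 to 0.5). The chance that at least one of the three dose arms does so is about 75%. A 20-point imbalance with d = 0.5 shifts one estimate by 0.20 × 0.5 = 0.10 SD.

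**Step 5: bias and type I error.** The SAP model was simulated with and without the statin term (four arms of 32, 3,000 runs per setting, p = 0.3 and 0.5, d = 0, 0.5 and 1.0). With a true effect of 0.6, mean estimates without the term ran from 0.594 to 0.602. With no effect, one-sided rejection ran from 0.039 to 0.056 without the term and from 0.040 to 0.054 with it. There is no average bias and no inflation.

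**Step 6: cost if status carries no information.** In the Step 3 setting with no group difference, the SE rises from 6.31 to 6.37, or 0.06/6.31 = about 1.0%. In the four-arm model it rises from 0.252 to 0.253.

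**The case against.** A pre-specified ANCOVA with the baseline value and the named stratification factor is valid as it stands. The comparisons are declared exploratory, random imbalance is already covered by the confidence interval, and baseline LDL-C absorbs part of the difference between statin groups. The gain rests on a share and a difference that the documents do not give, and the lipid algorithm in Protocol Appendix 3 is not shown. The visible criterion for an inadequate response is tied to the Day 1 value in both groups, which could narrow or widen the gap. All of this stands. It limits the size of the point, but does not make the added term wrong.

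Four stronger readings are tempting, and the documents do not support them.

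- A reader might infer that statin status fixes lipid treatment from Week 2 onward. It does not: "Initiation and dose adjustments will be determined by the lipid levels collected at Weeks 2, 4, 8, 12, and 18". Even the first dose in a naive subject depends on the Week 2 LDL-C.
- A reader might infer that the omission biases the lipid comparisons or invalidates their tests. Step 5 shows otherwise.
- A reader might want the term at every post-baseline visit on the same argument. Week 2 blood is drawn before study rosuvastatin is dispensed, while experienced subjects are still on their prior statin, so the switching argument does not reach Week 2.
- A reader might expect the term to separate aldafermin's lipid effect from lipid-lowering treatment. It cannot. If aldafermin raises LDL-C, more naive subjects on active drug would be expected to start rosuvastatin, or ezetimibe later. That treatment follows randomization, and a common main effect does not remove it. The descriptive summaries by statin use in SAP 5.4 would be more informative on that question.

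**Conclusion.** The point holds as a low-cost refinement. The lipid and lipoprotein ANCOVA omits a baseline factor that the plan already collects and that, by the trial's own rules, determines the Week 2 rosuvastatin starting rule and the stop time. The consequence is a modest loss of precision and unadjusted chance imbalance in exploratory comparisons. The gain is about 1% to 11% in interval width, and near 3% at a middling d of 0.5. Those figures rest wholly on the assumed share and difference. Only LDL-C was put into mg/dL; for HDL-C, triglycerides and lipoprotein particles the result is the SD-scale table, and their d may differ.

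**What to change.** In SAP 5.2, for total cholesterol, HDL-C, LDL-C, triglycerides and lipoprotein particles, specify an ANCOVA with treatment, baseline fibrosis stage, baseline value and baseline statin status (experienced or naive) as a main effect. Apply it at visits after Week 2, chiefly Week 24 and, through SAP 5.3, Week 30. Leave the other continuous endpoints as they are, and keep the SAP 5.4 summaries by statin use. State beside the model that the term does not adjust for LDL-C-driven rosuvastatin or ezetimibe.

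The cost is one model term and one degree of freedom, with an SE increase of about 1% or less if status proves uninformative. No new data are needed. The change should be made before unblinding, so that it cannot be read as a post hoc adjustment.
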